7 PROCEDURES

7.1 Procedures for Refraction and Vision Testing

Refraction and Vision Testing will be performed at all time-points specified in Sections 10.2 – 10.5 “Trial Assessments”.

For ETDRS testing, retroilluminated modified Ferris-Bailey ETDRS (Early Treatment Diabetic Retinopathy Study) charts are used starting at 4 meters (see Appendix 17.3).

When protocol refraction and best-corrected visual acuity measurement is required by the trial protocol, this will be performed only by certified visual acuity examiners. The examiner will be supplied with the previous protocol refraction only.

7.2 Tonometry

Tonometry will be performed at all time-points specified Sections 10.2 – 10.5 “Trial Assessments”. On days when two injections are given tonometry should be repeated after the first injection, to confirm perfusion of the optic nerve and return of IOP to ≤ 21 mmHg or within 5 mmHg of pre-injection before the second injection is administered. After the second injection, and also on days when only one injection is administered, IOP must return to < 30 mmHg before the subject leaves the clinic. For the post-injection tonometry, proper care should be taken to minimize the risk of contamination.

Goldmann applanation tonometry must be performed at Screening, Day 1, and Month 6/Early Withdrawal. Tono-Pen may be used at all other time-points, but Goldmann applanation tonometry must be used to verify IOP for a post-injection reading of ≥ 30 mmHg occurring more than 30 minutes post-injection, or for a reading of ≥ 30 mmHg at any other time.

7.3 Ophthalmologic Examination

The following examinations will be performed at all time-points specified in Sections 10.2 – 10.5 “Trial Assessments”.

- Inspection of the eyelids
- Examination of the extra-ocular muscle movement
- Inspection of the cornea
- Examination of the anterior chamber for inflammation (Appendix 17.1)

- Examination of the pupils
- Examination of the iris
- Inspection of the lens
- Inspection of the vitreous body (Appendix 17.2)
- Inspection of the retina and optic disc

7.4 Fundus Photography and Fluorescein Angiography

Color fundus photography (FP) and fluorescein angiography (FA) will be performed at all time-points specified in Sections 10.2 – 10.5 “Trial Assessments”.

The Sponsor will provide the Principal Investigator with instructions for the FP and FA as well as the submission process to the Reading Committee (RC).

7.5 Spectral Domain Optical Coherence Tomography (SD-OCT)

Spectral Domain optical coherence tomography (SD-OCT) will be performed at all time-points specified in Sections 10.2 – 10.5 “Trial Assessments”.

The Sponsor will provide the Principal Investigator with instructions for the SD-OCT as well as the submission process to the RC.

7.6 Laboratory Tests

The following laboratory tests will be performed as specified in Sections 10.2 – 10.5 “Trial Assessments”:

- Hematology: hemoglobin, platelet count, WBC and differential
- Renal Function: serum creatinine and BUN
- Hepatic function: serum bilirubin, alkaline phosphatase, GGT, SGOT/AST and SGPT/ALT
- Electrolytes: sodium, potassium, chloride, bicarbonate, calcium and phosphate
- Complete Urinalysis (including specific gravity, protein, and blood)
- Serum pregnancy test (for women of child-bearing potential)

If the Investigator judges a laboratory value outside of the normal range as clinically significant, the Investigator will repeat the laboratory determination as judged

appropriate to ensure the validity of the abnormal result. If any clinically significant abnormal results are noted, the tests are to be repeated until the results are normal, are no longer considered clinically significant by the investigator, or an explanation for the change is obtained.

7.7 Vital Signs and Physical Examination

A physical examination will be performed at Screening and at the Investigator's discretion thereafter. Assessment of vital signs will be performed at all time points specified in Sections 10.2 – 10.5 "Trial Assessments".

7.8 12- Lead Electrocardiogram (ECG)

A 12-Lead ECG will be performed at all time points specified in Sections 10.2 – 10.5 "Trial Assessments".

days prior to the first injection with a negative result. The two forms of effective contraception must be implemented during the trial and for at least 60 days following the last dose of test medication.

8.2.1.11 Provide written informed consent.

8.2.1.12 Ability to return for all trial visits.

8.3 Exclusion Criteria

Subjects will ***not be eligible for the trial*** if any of the following criteria are present in the study eye or systemically:

Ophthalmic Exclusion Criteria

- █ [REDACTED]
- █ [REDACTED]
- █ [REDACTED]
- █ [REDACTED]
- █ [REDACTED]
- █ [REDACTED]
- █ [REDACTED]
- █ [REDACTED]
- █ [REDACTED]
- █ [REDACTED]
- █ [REDACTED]
- █ [REDACTED]
- █ [REDACTED]
- █ [REDACTED]
- █ [REDACTED]
- █ [REDACTED]
- █ [REDACTED]
- █ [REDACTED]
- █ [REDACTED]
- █ [REDACTED]
- █ [REDACTED]

[REDACTED]

[REDACTED]

[REDACTED]

[REDACTED]

[REDACTED]

[REDACTED]

[REDACTED]

[REDACTED]

[REDACTED]

[REDACTED]

[REDACTED]

[REDACTED]

General Exclusion Criteria

8.3.1.16 Any of the following underlying diseases including:

- History or evidence of severe cardiac disease (e.g., NYHA Functional Class III or IV - see Appendix 17.5), history or clinical evidence of unstable angina, acute coronary syndrome, myocardial infarction or revascularization within last 6 months, ventricular tachyarrhythmia requiring ongoing treatment.
- History or evidence of clinically significant peripheral vascular disease, such as intermittent claudication or prior amputation.
- Stroke within 12 months of trial entry.
- Any major surgical procedure within one month of trial entry.

8.3.1.17 Subjects with a clinically significant laboratory value. Laboratory tests may be repeated once before randomization.

8.3.1.18 Previous therapeutic radiation in the region of the study eye.

8.3.1.19 Any treatment with an investigational agent in the past 60 days for any condition.

8.3.1.20 Women who are pregnant or nursing.

8.3.1.21 Known serious allergies to the fluorescein dye used in angiography, povidone iodine, to the components of the ranibizumab formulation, or to the components of the Zimura™ formulation.

9 TRIAL MEDICATION

9.1 Drug Supply

9.1.1 Zimura™

Zimura™ is a PEGylated RNA aptamer [REDACTED]

[REDACTED]

[REDACTED]

[REDACTED]

[REDACTED]

[REDACTED]

[REDACTED]

[REDACTED]

[REDACTED]

[REDACTED]

[REDACTED]

[REDACTED]

[REDACTED]

[REDACTED]

[REDACTED]

[REDACTED]

[REDACTED]

[REDACTED]

[REDACTED]

[REDACTED]

[REDACTED]

[REDACTED]

[REDACTED]

[REDACTED]

9.1.2 Lucentis® 0.5 mg

Lucentis® 0.5 mg is a recombinant humanized IgG1 kappa isotype monoclonal antibody fragment designed for intraocular use. Lucentis® 0.5 mg has a molecular weight of approximately 48 kilodaltons and is produced by an E. coli expression system in a nutrient medium containing the antibiotic tetracycline. Tetracycline is not detectable in the final product.

9.2 Dose and Administration

9.2.1 Preparation

Zimura™ and Lucentis® 0.5 mg will be injected without dilution.

Zimura™ is supplied in a single-use glass vial as noted in Section 9.1.1 above. [REDACTED]

Lucentis® 0.5 mg injection is a preservative-free colorless to pale yellow sterile solution, presented in a single-use glass vial or as a pre-filled syringe designed to deliver 0.05 mL of 10 mg/mL ranibizumab injection aqueous solution with 10 mM histidine HCl, 10% α, α-trehalose dihydrate, 0.01% polysorbate 20, pH 5.5. Lucentis® should be used without further dilution and administered in accordance with the package insert.

9.2.2 Treatment Regimen and Duration

There will be 4 dosing cohorts on this trial. Approximately 60 subjects will be enrolled; 10 subjects in cohorts 1 and 2, and 20 subjects in cohorts 3 and 4.

Cohort 1

Administered Day 1 – Month 5, in the following sequence, 2 days apart:

- D0: Lucentis[®] 0.5 mg/eye
- D2: Zimura[™] 4 mg/eye (administered as two injections of Zimura 2 mg)

Cohort 2

Administered Day 1 – Month 5, in the following sequence:

- Lucentis[®] 0.5 mg/eye followed by Zimura[™] 2 mg/eye on the same day

Cohort 3

Induction Phase: Administered Day 1 – Month 2, in the following sequence, 14 days apart:

- D0: Lucentis[®] 0.5 mg/eye followed by Zimura[™] 2 mg/eye on the same day
- D14: Zimura[™] 2 mg/eye

Maintenance Phase: Administered Month 3 – Month 5, in the following sequence:

- Lucentis[®] 0.5 mg/eye followed by Zimura[™] 2 mg/eye on the same day

Cohort 4

Induction Phase: Administered Day 1 – Month 2, in the following sequence, 14 days apart:

- D0: Lucentis[®] 0.5 mg/eye followed by Zimura[™] 2 mg/eye on the same day
- D14: Zimura[™] 2 mg/eye

Maintenance Phase: Administered Month 3 – Month 5, in the following sequence, 2 days apart:

- D0: Zimura[™] 2 mg/eye
- D2: Lucentis[®] 0.5 mg/eye followed by Zimura[™] 2 mg/eye on the same day

All subjects will have a final follow-up visit at Month 6.

The first 10 subjects will be enrolled into Cohort 1 according to the procedures noted below.

The first three subjects will be assigned to Cohort 1 (Lucentis[®] 0.5 mg and Zimura[™] 4 mg). Once the 3rd subject completes a safety period of one week after the first dose of Zimura[™] 4 mg without the occurrence of a dose limiting toxicity as defined in Section 9.2.3 Dose Limiting Toxicity, full enrollment of Cohort 1 may commence.

If a DLT occurs in one or more of the first 3 subjects assigned to Cohort 1, then the Ophthotech medical team will evaluate all available data and either discontinue Cohort 1 or enroll an additional three subjects (for a total of 6 subjects) in Cohort 1. If the three additional subjects are enrolled, and no additional DLT occurs once the second set of 3 subjects in Cohort 1 has reached one week after the first dose of Zimura[™] 4 mg/eye, full enrollment of Cohort 1 may commence. If one or more DLTs occur in the second set of 3 subjects, a discussion of safety data will be held among the Ophthotech medical team to review the observed toxicities and determine whether Cohort 1 may proceed.

Once Cohort 1 has been fully enrolled, or if enrollment has been stopped due to one or more DLTs, then enrollment in the remaining 3 cohorts may commence. Subjects will be randomized in a 1:2:2 ratio to Cohort 2, Cohort 3, or Cohort 4.

9.2.3 Dose Limiting Toxicity

9.2.3.1 Clinical Examination

- Visual acuity: loss of 4 or more lines (≥ 20 letters), Baseline through Week 1. This will not be considered a DLT if the vision loss is due to an event deemed related to the injection procedure by the investigator (e.g., vitreous hemorrhage).
- Clinically significant inflammation: defined as $> 3+$ according to the grading schedule as modified from the Hogan or Nussenblatt method. (Appendix 17.1 and 17.2)
- Tonometry: increase of intraocular pressure (IOP) from Baseline of ≥ 15 mmHg on two separate examinations at least one day apart excluding the day of injection, despite pharmaceutical intervention.

- Accelerated formation of cataract (not related to the injection procedure): progression of one unit from Baseline to Week 1 defined by the Age-Related Eye Disease Study (AREDS) Lens Opacity Grading Protocol as adapted from the Wisconsin Cataract Grading System where the same observer is used.
- Other severe ocular abnormalities not usually seen in subjects with NVAMD.

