6 TRIAL DESIGN

There will be 4 dosing cohorts on this trial. Approximately 60 subjects will be enrolled; 10 subjects in cohorts 1 and 2 and 20 subjects in cohorts 3 and 4.

Cohort 1

Administered Day 1 – Month 5, in the following sequence, 2 days apart:

- D0: Lucentis[®] 0.5 mg/eye
- D2: Zimura[™] 4 mg/eye (administered as two injections of Zimura 2 mg/eye)

Cohort 2

Administered Day 1 – Month 5, in the following sequence:

- Lucentis[®] 0.5 mg/eye followed by Zimura[™] 2 mg/eye on the same day

Cohort 3

Induction Phase: Administered Day 1 – Month 2, in the following sequence, 14 days apart:

- D0: Lucentis[®] 0.5 mg/eye followed by Zimura[™] 2 mg/eye on the same day
- D14: Zimura[™] 2 mg/eye

Maintenance Phase: Administered Month 3 – Month 5, in the following sequence:

- Lucentis[®] 0.5 mg/eye followed by Zimura[™] 2 mg/eye on the same day

Cohort 4

Induction Phase: Administered Day 1 – Month 2, in the following sequence, 14 days apart:

- D0: Lucentis[®] 0.5 mg/eye followed by Zimura[™] 2 mg/eye on the same day
- D14: Zimura[™] 2 mg/eye

Maintenance Phase: Administered Month 3 – Month 5, in the following sequence, 2 days apart:

- D0: Zimura[™] 2 mg/eye

- D2: Lucentis® 0.5 mg/eye followed by Zimura™ 2 mg/eye on the same day

All subjects will have a final follow-up visit at Month 6.

The first 10 subjects will be enrolled into Cohort 1 according to the procedures noted below.

The first three subjects will be assigned to Cohort 1 (Lucentis® 0.5 mg and Zimura™ 4 mg). Once the 3rd subject completes a safety period of one week after the first dose of Zimura™ 4 mg without the occurrence of a dose limiting toxicity as defined in Section 9.2.3 Dose Limiting Toxicity, full enrollment of Cohort 1 may commence.

If a DLT occurs in one or more of the first 3 subjects assigned to Cohort 1, then the Ophthotech medical team will evaluate all available data and either discontinue Cohort 1 or enroll an additional three subjects (for a total of 6 subjects) in Cohort 1. If the three additional subjects are enrolled, and no additional DLT occurs once the second set of 3 subjects in Cohort 1 has reached one week after the first dose of Zimura™ 4 mg/eye, full enrollment of Cohort 1 may commence. If one or more DLTs occur in the second set of 3 subjects, a discussion of safety data will be held among the Ophthotech medical team to review the observed toxicities and determine whether Cohort 1 may proceed.

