10 TRIAL CONDUCT

10.1 Subject Enrollment

Before recruitment of subjects into the trial, written Institutional Review Board (IRB) or Ethics Committee (EC) approval of the protocol and informed consent must be obtained.

Subjects who meet the eligibility criteria and have provided written informed consent will be enrolled in the trial. If any inclusion or exclusion criteria are not met, treatment with trial drug should not commence without prior written approval from Ophthotech Corp. or its designee.

Written informed consent must be obtained before any of the Screening procedures listed below are performed. However, if a routine office procedure (e.g. FA, OCT) is performed to diagnose NVAMD independent of this clinical trial, and subsequently the subject provides informed consent for this study, these procedures performed prior to informed consent may be used as screening assessments for this study, provided the 14-day period of screening evaluations is respected and provided the assessments are acceptable to the standards of the study. An explanation of the trial and discussion of the possible risks and discomforts will be given by the investigator.

For the Screening visit only, assessments can be broken into 2 days if necessary. For all other visits, all assessments indicated must be performed on the same day.

The RC will determine eligibility of all subjects prior to enrollment. Only those subjects who fulfill all eligibility criteria will be entered into the trial.

The following assessments will be performed during the study.

10.2 Trial Assessments – Cohort 1

The following dosing days apply to subjects in Cohort 1.

D0	D0 = The first day of dosing at each monthly timepoint.
D2	D2 = The second day of dosing, 2 days after D0.

The following evaluations, as outlined in the Study Assessments Chart (see Section 3), will be performed on the days specified below:

Note:

- **Concomitant Medications should be assessed at every study visit.**
- **Adverse events (AEs) should be assessed starting at Day 1 after the first dose of trial drug.**

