10.2.3 Day 1 (D2 Visit)

Pre-injection

- Protocol refraction and visual acuity (4 meters) using ETDRS chart (SE)
- Tonometry and Ophthalmologic Examination (SE)

Injection

- Zimura™ 2 mg/eye – **dose 1**
 - Indirect Ophthalmoscopy (SE) – 1 to 2 minutes after the injection to assure that the optic nerve is perfused.
 - Ophthalmologic exam/Tonometry (SE) – After the injection, to confirm perfusion of the optic nerve and return of IOP to ≤ 21 mmHg or within 5 mmHg of pre-injection.
- Zimura™ 2 mg/eye – **dose 2**

Post 2nd Injection

- Indirect Ophthalmoscopy (SE) – 1 to 2 minutes after each injection to assure that the optic nerve is perfused.
- Ophthalmologic exam/Tonometry (SE) – At least 30 minutes after the second injection, a full ophthalmologic exam must be performed and IOP must be < 30 mmHg before the subject leaves the clinic.

3-Day Post-Injection Safety Check (± 1 day)

- Telephone call to subject to ensure there are no signs or symptoms of retinal detachment or endophthalmitis.

10.2.4 Day 9 Visit – Subjects in the DLT cohort only. The DLT cohort is defined as the first 3-6 subjects (depending on if DLTs are noted) enrolled in Cohort 1.

- Vital signs
- Protocol refraction and visual acuity (4 meters) using ETDRS chart (SE)
- Ophthalmologic examination and Goldmann applanation tonometry (SE)
- Spectral Domain optical coherence tomography (SD-OCT) (SE)
- Laboratory tests

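### Only one scheduled Cohort 1 examination can count towards the two-examination IOP dose-limiting-toxicity rule before full enrolment may open, so a raised Day 9 reading can be left unresolved

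*Protocol*

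**What the plan says.** **Criterion.** The IOP item in Protocol 9.2.3.1 begins "Tonometry: increase of intraocular pressure (IOP) from Baseline of" at least 15 mmHg. The rise must be present "on two separate examinations at least one day apart excluding the day of injection" and must persist despite drug treatment.

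**Enrolment checkpoint.** Protocol 6, 9.2.2 and 11.1, and SAP 2.2, allow full enrolment of Cohort 1 when the third subject "completes a safety period of one week after the first dose of Zimura™ 4 mg" without a DLT. If a DLT occurs and a second set of three is enrolled, the condition is that "no additional DLT occurs once the second set of 3 subjects in Cohort 1 has reached one week after the first dose of" that dose. The observation period is therefore again one week.

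**Schedule.** Protocol 3 and 10.2 give Cohort 1 Lucentis on D0 and two Zimura injections on D2, then a three-day telephone check. The next contact is "10.2.4 Day 9 Visit – Subjects in the DLT cohort only", which includes Goldmann tonometry of the study eye and no injection. After that come the Month 1 D0 and D2 visits, both with injections.

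**Other clocks.** The visual acuity DLT runs "Baseline through Week 1", and the cataract DLT also ends at Week 1. Section 9.2.3.1 does not say which day Week 1 is counted from.

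**The concern.** A checkpoint built on stated DLT criteria should let each criterion be answered yes or no for each subject before it opens. For IOP the criterion asks for two qualifying examinations and the schedule supplies one. If the Day 9 reading is raised, the planned visits leave the subject neither a DLT nor clearly free of one. Read literally, no DLT has been recorded, so full enrolment is permitted.

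Safety is the trial's only objective, and the remaining Cohort 1 subjects would receive two Zimura injections in one eye at one visit. An unresolved pressure rise in one of the first three to six subjects is the kind of information the checkpoint exists to collect.

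**Working it through.** The plan states no figure to reproduce here, so the check is a count of visits followed by the timing.

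**1. Count up to the checkpoint, per subject** (Protocol 3, 10.2.2 to 10.2.4)

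| Contact | Tonometry | Injection | Counts for the IOP DLT? |
|---|---|---|---|
| D0 | Yes | Lucentis | No |
| D2 | Yes | Zimura, twice | No |
| Telephone check | No | None | No |
| Day 9 | Yes | None | Yes |

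Qualifying: 1. Required: 2. Shortfall: 2 − 1 = 1. The D2 pre-injection reading does not fill it: it is taken on an injection day and before any Zimura has been given.

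**2. Does staggered enrolment add a planned examination?** Every Cohort 1 visit from Month 1 to Month 5 is an injection day. With 30-day months, and subject 1 enrolled 0, 14, 30, 60 or 120 days before subject 3, the count for subject 1 at the checkpoint stays at 1. Over the whole trial the only qualifying planned examinations are Day 9 and Month 6 (or Early Withdrawal, for a subject who leaves).

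**3. When could an unscheduled confirming examination fall?** Protocol 10.2 says "D0 = The first day of dosing at each monthly timepoint" and puts D2 two days later, but Section 3 heads both columns Day 1. Two readings follow:

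- D0 is Day 1: D2 is Day 3, so Day 9 is 9 − 3 = 6 days after the first Zimura dose.
- D0 is day 0: D2 is day 2, so Day 9 is 9 − 2 = 7 days after it.

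The earliest confirming examination is one day later. For the third subject that is 6 + 1 = 7 days (on the checkpoint date) or 7 + 1 = 8 days (one day after it). For a subject enrolled s days before the third, it falls s days earlier relative to the checkpoint. At s = 2 or more it can precede the checkpoint on either reading. The planned-visit count is 1 on both readings.

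**4. How often would the gap matter?** Only if a checkpoint subject has a raised Day 9 reading. The documents give no rate, so p below is an assumption, with subjects taken as independent. The chance of at least one raised reading among n subjects is 1 − (1 − p)^n.

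| Assumed p | n = 3 | n = 6 |
|---|---|---|
| 5% | 1 − 0.95³ = 14.3% | 1 − 0.95⁶ = 26.5% |
| 10% | 27.1% | 46.9% |
| 20% | 48.8% | 73.8% |

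The n = 6 column applies only if the second set is enrolled, and assumes that pressure rises are unrelated to whatever triggered that set. These figures are the chance that the question arises. They are not the chance that a toxicity is missed.

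**The case against.** The best defence is that the criterion describes an event-driven sequence. Persistence despite treatment presupposes that a raised pressure was found, treated and measured again, and such a re-examination would naturally be unscheduled. SAP 3.3.1 and 3.3.2 provide for unscheduled visits, and Protocol 12.2 requires the investigator to treat adverse events. Opening enrolment is permitted, not compelled. This defence stands in part: a second reading may well be obtained in practice. But the visible text does not require one after a raised Day 9 reading and does not hold enrolment for it.

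A reader might go further than the documents allow in four ways:

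- *That the checkpoint is blind to IOP.* It is not. Each checkpoint subject has Goldmann tonometry at Day 9, and a reading that is not raised is evidence against a sustained rise. The gap is one-sided.
- *That confirmation can come only after the checkpoint.* Step 3 shows otherwise for subjects enrolled earlier, and for the third subject on the six-day reading it can fall on the date itself.
- *That this is the only protection against raised IOP.* Protocol 7.2 and 10.2 set pressure conditions before a second injection and before the subject leaves the clinic. Protocol 9.2.3 also keeps open routes for other severe ocular abnormalities and severe toxicity. The pressure conditions address rises on the day of injection, which the DLT rule excludes, and the open routes rely on judgement. Neither makes the IOP criterion itself assessable.
- *That the chance of declaring an IOP DLT is zero.* That is so only if unscheduled examinations are ruled out, and nothing rules them out.

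Appendix 17.4 is redacted and may add tonometry times. The Section 3 footnote mentions it alongside the measurements taken around injections, so extra non-injection-day readings look unlikely, but this cannot be confirmed.

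**Conclusion.** The mismatch is real and limited. Before the one-week checkpoint, planned visits supply one of the two examinations that the IOP criterion needs. They can support a finding of no sustained rise; they cannot alone establish an IOP DLT. A subject whose Day 9 reading is raised can be unresolved when full enrolment is permitted, and this is most likely for the last subject enrolled. It concerns three subjects, or six if the second set is used, and only those with a raised Day 9 reading.

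The conclusion rests on reading the injection-day exclusion as covering the whole of D0 and D2, and on the redacted appendix adding no visit.

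The six-or-seven-day ambiguity of Day 9, and the missing link between Week 1 and the enrolment clock, are minor labelling points. It would be too strong to say that the clocks contradict each other: the acuity and cataract items can be read as naming the two values to be compared, without fixing where the week starts.

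**What to change.** The sponsor should reconcile Protocol 9.2.3.1, the Cohort 1 schedule in Protocol 3 and 10.2 (repeated in SAP 3.1), and the enrolment text in Protocol 6, 9.2.2 and 11.1 and SAP 2.2. The aim is that every checkpoint subject's IOP DLT status is determined before full enrolment of Cohort 1 opens. The same clock should be stated in all these places, with Day 9 and Week 1 defined on it. Whether to change the criterion, the examinations or the checkpoint date is a clinical decision for the sponsor's medical team; no choice is proposed here.

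The cost is a protocol wording change with matching SAP text, and possibly a short delay at the checkpoint or one further pressure reading in at most six subjects.
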